RESEARCH PLAN: The goal of this proposal is to determine the efficacy of timed rectal evacuation as a treatment for anorectal dysfunction symptoms in patients with mild-to-moderate severe MS. The primary end-point of the randomized clinical trial is a greater than 30% improvement in patients' subjective global assessment of bowel symptom severity after 4 weeks. In secondary analyses, we will determine the factors predicting treatment response, as well as assess the impact of therapy on measures of global and anorectal dysfunction-related quality of life.

Study Design: This is a single-center, randomized, double-blind placebo controlled trial incorporated into routine clinical care for MS patients with anorectal dysfunction. Patients will be randomized to receive placebo or bisacodyl 10 mg rectal suppositories every other day for 4 weeks.

Study Population and enrollment: Patients at the University of Pittsburgh Medical Center (UPMC) MS Center with anorectal dysfunction will be recruited via either an existing registry, chart review, and/or ongoing care encounters. The UPMC MS Center currently cares for well over 2,000 patients. The study is adequately powered if enrollment reaches 56 patients (see Power Analysis below). To ensure adequate numbers in an intention-to-treat analysis, we will plan for a ~20% patient drop-out rate (thus, enrolling 70 patients in total). Normal clinical care pathways at UPMC naturally generate ~2-3 patient consultations per week for MS patients with anorectal dysfunction (total ~125 patients per year), and the pool of potential study candidates far exceeds that number. Therefore, enrollment of 70 patients appears quite feasible.

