During Phase 2, patients will meet the PI / Co-PI in the UPMC Digestive Disorders Center (DDC) for anorectal function testing (anorectal sensory and High Resolution Anorectal Manometry (HRAM) testing), which typically takes about 45 minutes. This is a one time, routine test that is performed in patients with anorectal dysfunction. It involves the transanal placement of a thin manometry catheter with inflatable balloon into the rectum. The patients' threshold to first sensation of rectal filling, urgency, and pain, basal anal resting pressure, voluntary anal squeeze pressure, and the rectal-anal inhibitory reflex (RAIR) to rectal distention and during simulated strain, as well as the ability to evacuate a 50 cc volume rectal balloon within one minute are all recorded variables and constitute normal components of such testing. The PI/Co-PI will meet with patients in the DDC GI lab around the time of the anorectal testing, and based on the clinical assessment of dominant bowel symptoms, provide patients with guidance on baseline interventions (either laxative or anti-diarrheal use). For example, the use of oral therapies is predicated on patients' typical stool form (using the Bristol Stool Scale 1-7) - the goal is to achieve a typical bowel movement of a 3-5 in consistency. Patients with Bristol 1-2 stools (hard) will use 8.5 - 42 grams of PEG-3350 laxative per day, while those with Bristol 6-7 (loose) will use 0.5 - 4 grams of loperamide per day, titrated to the goal. At the end of Phase 2 visit, patients will be given instructions on study medication use and will obtain the study drug (double-blinded; study drug "blister" packets would have been previously randomized by the pharmacy and delivered to the DDC). Patients will be encouraged to continue daily bowel diaries for the ensuing 4 weeks of the study trial period. Phase 2, including the physiological testing assessment and meeting with the PI/Co-PI, should take about 1.5 hours in total.

During the next 4 weeks, patients will use recommended oral therapies in addition to the every other day use of the rectal suppository study medication. They will record events in their daily bowel diary.

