- 2) Daily Bowel Diaries patients will record the consistency (Bristol Stool Scale, 1-7), number of bowel movements (BM), and occurrence of any fecal incontinence (FI) episodes each day. This data will be used to abstract BM and FI weekly frequency, as well as the mean change in stool consistency during the study period.
- 3) Patient Assessment of Constipation Symptom Questionnaire (PAC-SYM)
- 4) Fecal Incontinence Severity Index (FISI)
- 5) Patient Assessment of Constipation QOL (PAC-QOL)
- 6) Rockwood Fecal Incontinence Quality of Life Scale (FIQL)
- 7) SF-36 health status questionnaire
- 8) Study Medication Compliance
- 9) Anorectal Sensory and High Resolution Anorectal Manometry Testing: First sensation of rectal filling, urgency, and pain, basal anal resting pressure, voluntary anal squeeze pressure, and the rectal-anal inhibitory reflex (RAIR) to rectal distention and simulated strain, as well as the ability to evacuate a 50 cc volume rectal balloon within one minute.

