#### SECONDARY END POINTS:

1) Daily Bowel Diaries – patients will record the consistency (Bristol Stool Scale, 1-7), number of bowel movements (BM), and occurrence of any fecal incontinence (FI) episodes each day. This data will be used to abstract BM and FI weekly frequency, as well as the mean change in stool consistency during the study period.

- 2) Patient Assessment of Constipation Symptom Questionnaire (PAC-SYM)
- 3) Fecal Incontinence Severity Index (FISI)
- 4) Patient Assessment of Constipation QOL (PAC-QOL)
- 5) Rockwood Fecal Incontinence Quality of Life Scale (FIQL)
- 6) SF-36 health status questionnaire
- 7) Study Medication Compliance
- 8) Anorectal Sensory and High Resolution Anorectal Manometry Testing: First sensation of rectal filling, urgency, and pain, basal anal resting pressure, voluntary anal squeeze pressure, and the rectal-anal inhibitory reflex (RAIR) to rectal distention and simulated strain, as well as the ability to evacuate a 50 cc volume rectal balloon within one minute.
- 2.18 Describe the statistical approaches that will be used to analyze the study data.
  - \* Addressed below:

Categorical data will be analyzed using Fisher's Exact tests for differences in proportions. Continuous data will be analyzed using Student's t-tests to detect differences in group means, with Bonferroni correction for multiple comparisons. We will use logistic regression to determine the factors that predict treatment responses.

A p<0.05 will be used as the threshold for statistical significance in all cases.

POWER ANALYSIS/SAMPLE SIZE: It is generally regarded that a 3-point reduction represents a clinically meaningful change using such a 10 point scale, and similar research studies using patient-reported outcomes have reported standard deviations ranging around ~2.5 points. However, we do not have baseline data to estimate variance, and thus we took a conservative estimate with an expected standard deviation of 4 points. Given these assumptions, we will need 28 patients in each study arm to detect at least a 30% reduction in symptom severity, with a power of 0.80, alpha=P<0.05 in a two-tailed analysis.

[reviewer notes-]

- 2.19 Will this research be conducted in (a) a foreign country and/or (b) at a site (e.g., Navajo Nation) where the cultural background of the subject population differs substantially from that of Pittsburgh and its surrounding communities?
  - \* No

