# 4.14 Will you inform research subjects about the outcome of this research study following its completion?

\* Yes

If **Yes**, describe the process to inform subjects of the results:

Patients and the PI/Co-PI will be debriefed after Phase 3 by the study coordinator. They will then be seen by the PI/Co-PI in a standard follow up clinic visit. The debriefing is a necessary part of the patient's continuity of care, as it may direct changes in patient management (i.e. if a patient did not have a clinical improvement in the placebo arm, they may be offered study medication or its equivalent). As a patient reported outcome is the primary outcome measure, the "results" of the study should be self-evident to patients.

Section: Section 5 - Potential Risks and Benefits

[reviewer notes-]

5.1 Describe potential risks (physical, psychological, social, legal, economic or other) associated with screening procedures, research interventions/interactions, and follow-up/monitoring procedures performed specifically for this study:

\*

	Research Activity:	Bowel Diary
	Common Risks:	No Value Entered
View	Infrequent Risks:	All efforts will be made to keep the information secure. However, there is a small chance of a breach in confidentiality with any medical record keeping.
	Other Risks:	No Value Entered
	Research Activity:	Medical Record Review
	Common Risks:	No Value Entered
View	Infrequent Risks:	There is a small chance of a breach in confidentiality with any medical record review, either by Care Team staff as a part of routine care, or by the study coordinator in the process of

		accessing information from the "UPMC Multiple Sclerosis and Related Disorders Registry" (PRO12010609).
	Other Risks:	No Value Entered
	Research Activity:	Research Intervention
View	Common Risks:	The study medication, bisacodyl 10 mg rectal suppository, is available over-the-counter for routine use for constipation. Side effects of bisacodyl rectal suppositories include stomach discomfort, nausea, faintness, rectal burning, mild cramps, and diarrhea but these are potential issues are uncommon. There are no side effects to taking placebo, but patients could have a risk of continued bowel dysfunction if they do not receive the study drug.
	Infrequent Risks:	No Value Entered
	Other Risks:	No Value Entered
	Research Activity:	Screening and Enrollment

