#### Describe the benefit:

Most patients are likely to see some subjective improvement in bowel function (even those in the placebo arm), since all patients will be will be recommended to use some intervention to alter stool form (i.e. laxatives or anti-diarrheals). The study participants assigned to the active medication arm may derive subjectively greater improvement in bowel related symptoms (the primary hypothesis).

5.13 Describe the data and safety monitoring plan associated with this study. If the research study involves multiple sites, the plan must address both a local and central review process.

The Principal Investigator, [name], will meet with [name] (Co-PI) every 8 weeks to evaluate the progress of the research study, including assessment of data quality and subject recruitment.

Data and Safety will be further monitored by a joint meeting every 6 months between the PI, Co-PI, and [name], a nurse manager of the UPMC MS Clinic who oversees clinical trials for the group. This group will be responsible for the following: 1) reviewing the data accumulated from the ongoing study; 2) advising the principal investigator or study sponsor of necessary changes to elements of the study that affect subject safety; 3) determining whether there has been any change to the risk-to-benefit assessment during the course of the study; and 4) determining whether the study should continue as designed. They will also review, on an ad hoc basis, any serious adverse events (SAE) that are directly related to the study medication as given according the study protocol. The results of the DSMB meetings will be submitted to the IRB at the time of the annual renewal.

[reviewer notes¬]

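### Loose-stool days, a named side effect that the daily diary can show, can be hidden in the mean change in stool form, and no summary of non-serious harms by arm is specified

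*Combined protocol and SAP*

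**What the plan says.** Section 5.1 (Research Intervention) states: "Side effects of bisacodyl rectal suppositories include stomach discomfort, nausea, faintness, rectal burning, mild cramps, and diarrhea". It goes on to describe such effects as uncommon.

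Under Study Measures in Section 2.6, the diary is a daily record: "patients will record the consistency (Bristol Stool Scale, 1-7), number of bowel movements (BM), and occurrence of any fecal incontinence (FI) episodes each day". It is kept for 2-4 weeks after study entry, and patients are encouraged to continue it over the 4 treatment weeks, so each patient can supply a baseline.

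Section 2.17, item 1, names three uses of these data: "This data will be used to abstract BM and FI weekly frequency, as well as the mean change in stool consistency during the study period". Section 2.18 adds the method: "Continuous data will be analyzed using Student's t-tests to detect differences in group means, with Bonferroni correction for multiple comparisons".

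Two design features in Section 2.6 bear on this. For stool form, "the goal is to achieve a typical bowel movement of a 3-5 in consistency"; the same paragraph classes Bristol 1-2 as hard and 6-7 as loose. For dosing, "Patients will be randomized to receive placebo or bisacodyl 10 mg rectal suppositories every other day for 4 weeks".

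On safety, Section 5.1.1 has the coordinator contact patients about problems. Section 5.13 has a six-monthly joint review of accumulated data and of the balance of risk and benefit, and adds: "They will also review, on an ad hoc basis, any serious adverse events (SAE) that are directly related to the study medication". No end point in Section 2.17 is an adverse event, and Section 2.18 gives no method for tabulating harms.

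**The concern.** Stool form on the Bristol scale is good in the middle and bad at both ends. A mean over days treats it as a quantity on which high and low values may offset each other, so a patient who alternates between hard and loose stool can have the same mean as one with normal stool every day. Every-other-day dosing makes an alternating pattern plausible in the active arm.

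The other two diary summaries do not fill the gap. More bowel movements may read as benefit in a constipated patient, and a loose stool that brings neither an extra movement nor leakage appears in neither frequency. Mean incontinence frequency in an arm can fall while some patients get worse.

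The trial aims to support a treatment algorithm described as safe (Section 1.2) and enrols patients with fecal incontinence (Section 3.13), for whom induced loose stool matters. Non-serious diarrhea has no specified route into the results by arm, although the data that could show it are being collected.

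**Working it through.** **1. The plan's own figure.** The documents give no figure for diarrhea or loose-stool days. The only sample-size figure is for the primary outcome (Section 3.12): difference 3, SD 4, two-sided alpha 0.05, power 0.80. The normal formula gives n per arm = 2 × (1.960 + 0.842)² × 4² / 3² = 27.9, so 28, as stated. Allowing for 20% drop-out, 56 / 0.80 = 70, or 35 per arm. Nothing below changes these.

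**2. What a 28-day mean can show.** Four weeks is 28 days, and dosing every other day gives 14 suppository days. If k days have form L and the rest form r:

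mean = [k × L + (28 − k) × r] / 28.

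The daily patterns are assumptions; the documents give none. The target is 3-5 and loose is 6-7 (Section 2.6).

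| Baseline | Loose days k | Form on loose days | Form on other days | Mean | Change | Mean within 3-5? |
|---|---|---|---|---|---|---|
| 2 | 4 | 6 | 2 | 2.57 | +0.57 | no, still below |
| 2 | 7 | 6 | 2 | 3.0 | +1.0 | yes |
| 2 | 14 | 6 | 2 | 4.0 | +2.0 | yes |
| 2 | 21 | 6 | 2 | 5.0 | +3.0 | yes |
| 2 | 14 | 6 | 3 | 4.5 | +2.5 | yes |
| 4 | 14 | 6 | 4 | 5.0 | +1.0 | yes, at the edge |
| 4 | 14 | 7 | 4 | 5.5 | +1.5 | no, above |
| 6 | 14 | 7 | 6 | 6.5 | +0.5 | no, visibly worse |

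For example, row three is (14 × 6 + 14 × 2) / 28 = 112 / 28 = 4.0, the same mean as form 4 on all 28 days, although half the days were loose.

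Masking can therefore be complete in patients with hard stool at baseline and frequent loose days, is partial in those with normal form, and is absent in those who start loose.

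**3. What a by-arm comparison could deliver.** Suppose patients are classed as having diarrhea or not and the arms are compared by Fisher's exact test (two-sided 0.05, full enumeration). The rates are assumptions.

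| Placebo vs active | Power, 28 per arm | Power, 35 per arm |
|---|---|---|
| 5% vs 15% | 0.08 | 0.14 |
| 5% vs 20% | 0.21 | 0.33 |
| 10% vs 30% | 0.33 | 0.46 |
| 10% vs 40% | 0.66 | 0.79 |

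Even a 30-point difference does not reach 0.80 at full enrolment. This supports estimates with intervals, not a test.

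**The case against.** A reader might infer that drug-induced diarrhea would be reported as normalised stool, or not at all. The documents do not support that.

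- The plan reports a mean change and never says that a mean of 3-5 will be called normal. That range is the titration goal for oral therapy, not an analysis threshold.
- Worsening has other planned readouts: bowel-movement and incontinence frequency, FISI, FIQL and the primary severity rating. Coordinator contacts and the six-monthly review could also bring cases to light.
- The alternating 2/6 pattern assumes that oral laxative has no effect on the other days, whereas Section 2.6 titrates it to the 3-5 goal. Masking also depends on baseline form.
- Section 5.1 calls these effects uncommon, so large differences between arms should not be presumed.
- The diary pages are an attachment not reproduced here. It is not stated that each stool is rated, or that dosing days are recorded.

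All of this stands, and it limits the point. It does not remove it. The other readouts do not identify loose stool, and nothing says that cases raised with the coordinator are recorded or tabulated by arm. Partial success of oral therapy does not restore the signal either: with the other days at form 3, the mean in the example is 4.5, still inside the target.

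**Conclusion.** The point holds in a limited form: loose-stool days can be hidden in the only planned summary of stool form, and the plan specifies no by-arm summary of non-serious harms. In the assumed patient starting at Bristol 2, loose stool on 25%, 50% or 75% of days gives means of 3.0, 4.0 and 5.0. With 4 of 28 days loose the mean is 2.57, still below the target, and a patient who starts at 6 shows worsening. How often such patterns would occur cannot be judged from the documents.

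A reader might also infer that a direct comparison of loose-stool patients would be adequately powered. It would not be at plausible differences: power is 0.21 to 0.33 for 5% versus 20%, and reaches 0.79 only for 10% versus 40% with all 70 patients evaluable. The primary analysis and sample size are unaffected. The change is worth making because it is cheap and uses a daily record and a loose-stool category that the protocol already has.

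**What to change.** Keep the mean change. In Sections 2.17 and 2.18 add, by arm:

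1. the proportion of recorded diary days at Bristol 6-7 on treatment, and its change from the patient's own baseline diary;
2. the number of patients whose weekly frequency of incontinence days increased from baseline, including those with none at baseline.

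Give both with 95% confidence intervals. Label them descriptive safety outcomes, outside the Bonferroni family, and claim no power for them. Use form per day as the diary records it, and report how many days were recorded, since diary keeping on treatment is only encouraged. Split by suppository day only if dosing days are recorded. Fix the definitions before the first allocation is revealed: Section 2.6 has allocation disclosed to each patient and the investigators at Phase 3, so a harm definition chosen later would be chosen by people who know the arms.

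The cost is two tabulations and a few lines of text, with no extra visits or patients and no change to any dose or clinical rule. The downside is two more descriptive comparisons, with some background loose days in both arms from oral laxative titration. The contrast between arms, not the level in one arm, is therefore what should be read.

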# 1.3 Background: Briefly describe previous findings or observations that provide the background leading to this proposal.

There is growing recognition that the factors driving multiple sclerosis (MS)-related disability extend beyond impairments in mobility to include both psychological and physical symptoms that negatively impact patients' quality of life. Anorectal dysfunction, broadly defined as the presence of chronic constipation and/or fecal incontinence, is a common symptom experienced by MS patients that is often ranked as negatively impactful on quality of life as impaired mobility. About 40% of MS patients suffer from chronic constipation, while ~25% of patients experience frequent episodes of fecal incontinence. Mixed forms of anorectal dysfunction are less common, occurring in at least 10-15% of MS patients, but pose a particular therapeutic challenge. Because of the daily impact of these common symptoms, anorectal dysfunction places a tremendous burden on MS patients and their caregivers.

Normal defecation patterns require precise conscious and unconscious sensorimotor functions to support the perception of rectal filling, to retain stool in the rectum without anal leakage, and to allow for volitional elimination of stool without difficulty. MS patients may be especially prone to developing anorectal dysfunction because even subtle impairments in sensation from the anorectum and/or the timing and efficacy of coordinated abdominal, pelvic floor, and anal muscle contractions are sufficient to generate symptoms. Regardless of subtle differences in the underlying mechanisms that lead to anorectal dysfunction in any one MS patient, an ideal therapeutic approach should be safe, flexible, straightforward, and effective enough to help most patients.

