MS patients with mild to moderately severe disease (MSIS-29 Physical domain scores <61 or an equivalent EDSS < 6.5) aged 18-80, of any gender, disease subtype, duration of illness, or with any current use of disease modifying therapy and who also have anorectal dysfunction (chronic constipation and/or fecal incontinence) are eligible. MSIS-29 and EDSS scores are determined in the course of routine MS care at UPMC.

3.14 Exclusion Criteria: List the specific criteria for exclusion of potential subjects from participation.

MS patients with severe disease, as assessed by MSIS-29 Physical domain scores greater than 61 or an equivalent EDSS of greater than 6.5), aged <18 or >80, or patients with surgically altered anorectal anatomy (i.e. proctectomy/partial colectomy, ostomy creation), active enteric infection (i.e. Clostidium Difficile), or inflammatory bowel disease (i.e. ulcerative proctitis) will be excluded.

3.15 Will HIV serostatus be evaluated specifically for the purpose of participation in this research study?

\* No

If **Yes**, provide a justification:

Section: Section 4 - Recruitment and Informed Consent Procedures

[reviewer notes¬]

**4.1** Select all recruitment methods to be used to identify potential subjects: Research Registry

Other Strategies: Described below

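### The stool-consistency end point is a mean change on a scale that is abnormal at both ends, so in this mixed population it cannot be read as benefit or harm

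*Combined protocol and SAP*

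**What the plan says.** Section 2.17 lists the daily bowel diary as the first secondary end point, and section 2.6 (Study Measures, item 2) describes it in the same terms. Three summaries come from it: weekly bowel-movement frequency, weekly incontinence frequency, "as well as the mean change in stool consistency during the study period". Consistency is scored on the Bristol scale from 1 (hard) to 7 (loose). Section 2.18 compares continuous measures between arms by t-test on group means, with a Bonferroni correction.

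Section 3.13 admits MS patients "who also have anorectal dysfunction (chronic constipation and/or fecal incontinence) are eligible". Section 2.6 (Phase 2) assigns oral therapy by typical stool form. "Patients with Bristol 1-2 stools (hard) will use" an oral laxative, "while those with Bristol 6-7 (loose) will use" an anti-diarrheal, and "the goal is to achieve a typical bowel movement of a 3-5 in consistency".

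The plan does not define an absolute change, a distance from the 3-5 band, a proportion of stools within it, or an analysis split by baseline stool form. It does not describe randomisation as stratified by stool form.

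**The concern.** The goal lies in the middle of the scale, and patients start on both sides of it. Two points up is success for a patient who starts at Bristol 2. Two points down is success for one who starts at 6. Averaging signed changes adds these successes with opposite signs. It does the same with failures: a move from 2 to 1 offsets a move from 6 to 7.

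Stool form is the only diary summary that shows whether stool was normalised, which is half of the strategy described in section 1.4. As the end point stands, a mean near zero could mean that nothing happened, or that both groups moved towards the goal. A positive difference between arms could be relief of hard stools or aggravation of loose ones.

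**Working it through.** **The plan's own figure.** No sample size or effect size is given for stool consistency. The only stated figure is for the primary end point (section 3.12: difference 3, SD 4, two-sided alpha 0.05, power 0.80). It reproduces: n = 2 × [4 × (1.960 + 0.842) / 3]² = 27.9, so 28 per arm, 56 in total, and 56 / 0.80 = 70 enrolled. Nothing below changes it.

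**Step 1: mean within an arm.** Let p be the share of patients with hard stools. Assume that every hard-stool patient goes from 2 to 4 and every loose-stool patient from 6 to 4, so that all reach the goal.

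- Mean signed change = p(+2) + (1 − p)(−2) = 4p − 2
- Variance due to the mix alone = 16p(1 − p)

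| Hard share p | Mean change | SD from mix | At goal |
|---|---|---|---|
| 50% | 0.0 | 2.00 | 100% |
| 60% | +0.4 | 1.96 | 100% |
| 70% | +0.8 | 1.83 | 100% |
| 100% | +2.0 | 0 | 100% |

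The mix is not stated. Section 1.3 says: "About 40% of MS patients suffer from chronic constipation, while ~25% of patients experience frequent episodes of fecal incontinence". If 40:25 is taken as a rough proxy, p = 40/65 = 0.615 and the mean is 4 × 0.615 − 2 = +0.46, against 2 points of real movement per patient. The proxy is weak, because those are symptom rates and incontinence is not the same as loose stool.

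**Step 2: a shift in one direction.** Suppose a treatment softens every patient's stool by one point. The mean change is p(+1) + (1 − p)(+1) = +1 at any mix, so nothing cancels. But the Bristol 2 patients move to 3, inside the band, while the Bristol 6 patients move to 7, further outside it. The same +1 is benefit for a share p and harm for a share 1 − p.

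**Step 3: dilution between arms.** This is a simulation at 28 per arm. None of the following inputs comes from the documents: hard baselines of 1 or 2, loose baselines of 6 or 7, 80% versus 40% of patients normalised to 4, noise SD 0.75, alpha 0.05 without Bonferroni.

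| Hard share | Mean signed difference | Power, signed t-test | Power, distance from 3-5 | Power, in band (Fisher) |
|---|---|---|---|---|
| 100% | 0.94 | 0.73 | 0.66 | 0.65 |
| 80% | 0.55 | 0.21 | 0.66 | 0.65 |
| 61.5% | 0.22 | 0.06 | 0.66 | 0.64 |
| 50% | 0.00 | 0.05 | 0.66 | 0.65 |

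The last column classes each patient as inside or outside the band, a simpler measure than a proportion of stools. The signed measure does slightly better when all patients have hard stools, and loses most of its power at 80% hard. The band-based measures hold steady at every mix.

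**Step 4: chance imbalance in mix.** With complete success in both arms, a 50:50 mix in one and 60:40 in the other gives a difference of 0.4. The standard error is √[(4.00 + 3.84) / 28] = 0.53, so t = 0.4 / 0.53 ≈ 0.76 and p ≈ 0.45.

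**The case against.** The strongest objection is that the opposite-direction push is not the randomised treatment. It comes from oral therapy, titrated to the goal in section 2.6 and recommended to patients in both arms (section 5.12). Only the suppository is randomised. A reader might infer from Step 1 that a true suppository benefit would show as zero. The documents do not support that. It would require the suppository itself to move stool form in opposite directions in the two groups, or to change how far normalisation goes, and no section predicts either. A shift in one direction would not cancel, and the t-test could detect it. This stands, and it limits full cancellation mainly to the within-arm mean. It does not rescue interpretation, as Step 2 shows.

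A reader might also take a different hard-to-loose mix between arms as bias. It is not. Under randomisation it is sampling noise, and Step 4 shows that the planned test absorbs it. What remains is the added variance.

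Three further points are fair. The mix is unknown, and the examples leave out patients already at 3-5; if loose-stool patients are few, cancellation is small. The 80% versus 40% contrast is illustrative, and a gap that wide is hard to expect when both arms are titrated to the same goal. The word signed is inferred; but it is the ordinary meaning of a mean change and nothing overrides it, so if something else was intended the text still needs to say so.

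Finally, this is one of three summaries within one of eight secondary items, and Aim 2 gives key status to quality of life. That limits the importance of the point but does not remove it.

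**Conclusion.** The concern holds in a limited form. As written, the stool-consistency summary cannot be read as benefit or harm in a population that starts on both sides of the 3-5 goal. That conclusion needs only the scale, the goal and the eligibility rule, all of which are in the documents.

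The size depends on the mix, which is not. With complete success inside an arm, the mean runs from 0.0 at 50:50 to +0.8 at 70:30, against 2 points of movement per patient. Between arms, a normalising difference would be diluted, severely in the simulated case once a fifth or more of patients have loose stools, but the real effect may be small or one-directional. The point does not show that the end point will be null or that the comparison is biased, and it does not touch the primary end point or the sample size.

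**What to change.** In sections 2.6 and 2.17, define the stool-consistency end point as each patient's proportion of diary stools at Bristol 3-5 during the 4 treatment weeks. Compare it between arms with the baseline-diary proportion taken into account, for example as a covariate. If the diary form records one consistency per day, use days instead of stools. Report the signed change only as description, separately for patients with hard (1-2) and loose (6-7) stools at baseline.

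Distance from the 3-5 band, scored 0 inside it, is an alternative but not an equivalent. A move from Bristol 1 to 2 shortens the distance from 2 to 1 and leaves the proportion at zero. One measure should be chosen in advance.

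The cost is a wording change. The diary is already collected at baseline and on treatment, and no treatment, visit or sample size changes. The downside is that the proportion ignores movement that stays outside the band. Because the baseline diary precedes the oral-therapy guidance, change from baseline will largely reflect background treatment on any measure, so the comparison between arms is the one to interpret.
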